#### 4.5 fNIRS Data Analysis

The fNIRS data will undergo preprocessing (performed in MATLAB) including filtering (to remove noise and drift), motion artifact correction, and segmentation of the task period. For each participant and each session (baseline, 3m, 6m), we will derive summary metrics such as the average oxyhemoglobin concentration change ( $\Delta[\text{HbO}_2]$ ) in specific regions of interest during the cognitive task relative to rest baseline. We might average signals over channels covering the left orbitofrontal cortex (OFC), right OFC, ventrolateral PFC, etc., based on the sensor layout. These ROI-level  $\Delta\text{HbO}_2$  will be the variables used for analysis.

**Longitudinal ROI Analysis:** Using GEE, we will model  $\Delta\text{HbO}_2$  as the outcome with group, time (0, 3, 6 months), and group $\times$ time as factors, similar to other outcomes. We anticipate, for instance, a significant group $\times$ time effect in left OFC  $\text{HbO}_2$ , indicating the intervention group's  $\text{HbO}_2$  increases over time relative to control (as observed in preliminary analyses). If GEE shows significance, we will follow up with post-hoc tests of group differences at 3 and 6 months, and time differences within each group. If data are normally distributed and complete, an LMM could also be used for confirmation. If some fNIRS measurements are missing (due to technical issues or dropouts), GEE can handle missing under MAR assumptions.

**Correlation with Clinical Outcomes:** We will compute Pearson or Spearman correlations between changes in fNIRS metrics (e.g.,  $\Delta\text{HbO}_2$  from baseline to 6m in a region) and changes in clinical scores (e.g., PHQ-9 drop) across individuals. A positive correlation would indicate that participants with larger brain activation increases tended to have greater depression improvement, supporting fNIRS as a biomarker. A small p-value would suggest significance of this correlation.

**ROC Analysis:** One key exploratory analysis is to evaluate whether fNIRS measures can classify depression status. We will define a binary variable for depression at 6 months (for

example, PHQ-9  $\geq 10$  indicating clinically significant depressive symptoms vs  $< 10$  indicating minimal symptoms). We will then take certain fNIRS measures (like the 6-month left OFC HbO2 level or the change in that level from baseline) and perform ROC curve analysis. The area under the ROC curve (AUC) will be calculated to assess discrimination ability. If AUC is significantly above 0.5, it indicates some predictive value. We will identify the optimal cutoff on the fNIRS measure that maximizes Youden's J (sensitivity + specificity - 1). For that cutoff, we will report sensitivity, specificity, positive predictive value, and negative predictive value. To account for sample variability, we will use a bootstrap approach (e.g., 1000 bootstrap samples of the data) to derive a confidence interval for the AUC and for the sensitivity/specificity at the chosen cutoff. For example, in preliminary findings, a cutoff  $\Delta$ HbO2 of approximately -0.47 mmol·mm in left OFC was identified for the experimental group depression prediction; we will verify if similar thresholds emerge and their stability via bootstrapping. This analysis is exploratory and aimed at generating hypotheses for future larger studies on using fNIRS as a screening tool.

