(e.g. left orbitofrontal cortex, ventrolateral PFC) and how these values change from pre- to post-intervention. Prior studies suggest that greater increases in prefrontal HbO₂ activation correspond to better emotional and cognitive outcomes [26]. We will explore whether our intervention group shows increased HbO₂ responses over time relative to controls, and whether certain threshold values of HbO₂ change can distinguish participants with resolved depression from those with persistent depression by 6 months. These **fNIRS measurements** are considered an exploratory outcome and will not be used as primary endpoints, but rather to supplement and biologically contextualize the clinical findings.

All outcome instruments (questionnaires and cognitive tests) are administered in the Vietnamese language by research staff. Standardized, validated Vietnamese versions are used for all scales (e.g. the PHQ-9 and MMSE have validated translations). For quality control, the same instruments are used at each follow-up, and staff members were trained to maintain consistency in administration.

Schedule of Events (Study Timeline)

The schedule of enrollment, interventions, and assessments is based on SPIRIT guidelines and is summarized below:

- **Screening & Baseline (Month 0):** Potential participants are screened against inclusion/exclusion criteria and provide written informed consent. At enrollment (pre-intervention baseline), we collect demographic information and stroke history (including stroke type, time since onset, lesion location, disability status by Modified Rankin Scale, etc.). Baseline assessments include the PHQ-9, FSS, MMSE, Barthel Index, and SIS administered via interview, as well as the first fNIRS measurement during a cognitive task. After baseline assessments, participants are randomized to either the intervention or control group. For those in the intervention arm, the first MI session typically occurs immediately or within a week after randomization, and the home-based rehab program is initiated with a visit scheduling within the first week.

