- **6-Month Follow-up (Month 6, end of study):** At the end of the 6-month study period, all participants undergo the final evaluation. The same battery of outcome measures (PHQ-9, FSS, MMSE, Barthel Index, SIS) is administered, and the **final fNIRS** measurement is conducted. The 6-month outcomes represent the primary endpoint for evaluating intervention effectiveness. By this time, the intervention group has concluded all activities (the last home visit by the physical therapist typically occurs around month 5 or 6 with the monthly schedule). We document any post-study referrals or ongoing care plans for both groups. After completing the 6-month assessment, participants are thanked and exit the study. Those in the control group are offered an opportunity to receive the intervention program after study completion, if appropriate, as an ethical consideration.

Sample Size and Justification

The sample size was determined based on detecting a clinically meaningful difference in depression outcomes between the two groups at 6 months. Using a two-sample comparison of mean change in PHQ-9 scores (intervention vs control), we assumed a difference in mean PHQ-9 reduction of approximately 3.43 points with a standard deviation of about 5.5, based on prior research on post-stroke depression interventions [27]. With a two-sided $\alpha=0.05$ and power (1– β) of 0.80, the estimated minimum sample required was 43 patients per group (calculated via the formula for comparing two means). We planned to enroll 46 patients in each group (total N=92) to account for potential drop-outs and ensure adequate power. This sample size also offers >80% power to detect medium-to-large effects on secondary continuous outcomes like FSS and Barthel Index, given similar variance assumptions. The actual achieved sample size was 92, which meets these targets. No interim analyses for efficacy were planned (due to the relatively short intervention duration and moderate sample size), so the full sample contributes to the final analysis.

Randomization, Allocation Concealment, and Blinding

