## 1. Introduction and Study Overview

This Statistical Analysis Plan (SAP) describes in detail the planned analytical approaches for the above-mentioned randomized controlled trial. The study's objective is to evaluate the efficacy of a 6-month intervention combining Motivational Interviewing (MI) and a home-based rehabilitation program versus standard care in improving post-stroke outcomes. A total of 92 stroke patients were randomized (1:1) to the intervention or control group. Outcomes are measured at baseline, 1 month, 3 months, and 6 months post-intervention. The primary outcomes include depression (PHQ-9 score), fatigue (FSS score), cognitive function (MMSE score), and physical function (Barthel Index). Secondary outcomes include quality of life (Stroke Impact Scale) and exploratory fNIRS-based biomarkers of cortical activity. No interim analyses were conducted; all analyses described here are post-finalization of data collection. This SAP is finalized prior to unlocking the database to avoid data-driven decisions.

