#### Secondary Outcomes:

- **Quality of Life:** Stroke Impact Scale (SIS) 3.0 overall score (0–100, higher = better). Change in SIS from baseline to 6 months will be compared between groups. SIS subdomains (physical, emotion, communication, etc.) might also be explored for additional insights, but the overall score is the main focus.

- **Functional Near-Infrared Spectroscopy (fNIRS) Biomarkers:** Several exploratory endpoints derive from fNIRS measurements of cortical hemodynamics during a cognitive task:

- Mean or peak change in oxyhemoglobin ( $\Delta\text{HbO}_2$ , measured in  $\text{mmol}\cdot\text{mm}$  or arbitrary units) in predefined regions of interest (e.g., left orbitofrontal cortex, right orbitofrontal cortex, dorsolateral prefrontal cortex) at baseline, 3 months, and 6 months.
- The change in  $\Delta\text{HbO}_2$  from baseline to 6 months for those regions.

- We will specifically evaluate if the intervention group shows a greater increase in  $\Delta\text{HbO}_2$  in the left orbitofrontal cortex over time compared to controls, as prior evidence suggested a link between orbitofrontal activation and depression improvement.

- **Derived binary outcomes for ROC analysis:** e.g., “6-month depression status” (yes/no based on PHQ-9 threshold as noted) and using fNIRS metrics (such as 6-month  $\Delta\text{HbO}_2$ ) as predictors.

- **Other Clinical Measures:** If collected, the Modified Rankin Scale (mRS) for disability and NIH Stroke Scale (NIHSS) at baseline will be described but not tested as outcomes. The trial registration did not include these as outcomes, but baseline differences will be accounted for if necessary.

**Safety Outcomes:** The study will note any adverse events (AEs) or serious adverse events (SAEs) reported during the 6-month period, such as falls, medical complications, or psychological distress. Given the nature of the intervention, we do not anticipate intervention-related SAEs. AEs will be coded and summarized by group (e.g., number of falls during follow-up, any hospitalizations, etc.). No formal hypothesis testing on safety outcomes is planned due to expected low incidence and lack of power for such events.

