## 4. Statistical Methods

### 4.1 General Analysis Principles

All statistical tests will be two-sided with a significance level of  $\alpha = 0.05$ . Outcomes will be analyzed primarily in the ITT population. We will use **descriptive statistics** to summarize baseline characteristics and outcomes at each time point by group. For continuous variables, we will report means and standard deviations (or medians and interquartile ranges if non-normal). Categorical variables will be summarized as counts and percentages. No formal hypothesis testing will be performed on baseline characteristics (any baseline differences observed will be noted but understood as chance differences due to randomization). Where relevant, 95% confidence intervals (CIs) will be provided for estimated effects (e.g., mean differences, odds ratios). All analyses will be conducted using Stata (v16.0) and R statistical software. fNIRS signal processing will utilize MATLAB with the NIRSIT toolbox, with processed outputs then analyzed in Stata/R.

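### The left OFC fNIRS effect is planned as a test of a predefined region, but the SAP says it was already seen in preliminary analyses of unstated origin, and the regions and metric remain open

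*SAP*

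**What the plan says.** SAP 3 (Secondary Outcomes) defines the fNIRS endpoint as the mean or peak change in oxyhemoglobin "in predefined regions of interest (e.g., left orbitofrontal cortex, right orbitofrontal cortex, dorsolateral prefrontal cortex". It then names left OFC as the region in which a greater increase under intervention will be specifically evaluated, and gives prior evidence as the reason.

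SAP 4.5 (Longitudinal ROI Analysis) expects a significant group-by-time effect in left OFC, with the intervention group rising relative to control, "as observed in preliminary analyses". A significant GEE result leads to post-hoc tests between groups and over time. SAP 4.5 (ROC Analysis) cites a preliminary left OFC cutoff of about -0.47 for depression prediction in the experimental group, and plans to verify whether similar thresholds emerge and are stable under bootstrapping.

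The Protocol (Outcome Measures, Neuroimaging Biomarkers) gives its regions as "e.g. left orbitofrontal cortex, ventrolateral PFC".

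On timing, SAP 1 states that no interim analyses were conducted and that "This SAP is finalized prior to unlocking the database to avoid data-driven decisions". On error control, SAP 4.1 says "All statistical tests will be two-sided with a significance level of" 0.05. SAP 4.7 leaves the four primary scales unadjusted and calls secondary outcomes exploratory. No rule is given for multiple regions or metrics.

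**The concern.** The region, contrast and direction of the planned test are those of the preliminary result. A result seen in one set of data and tested again in the same data, or in data that overlap, has not been confirmed. Bootstrapping a cutoff in the data that produced it measures its sampling variability but does not verify it. A reader of SAP 3 alone would take left OFC to be a region chosen in advance on outside evidence.

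The open list of regions and metrics is a second and separate problem. Several different sets of fNIRS results would all comply with the plan, and nothing obliges the authors to show the ones that are not highlighted.

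At stake is how secondary objective 2 and the fNIRS hypothesis in the Protocol are reported. The four primary outcomes (PHQ-9, FSS, MMSE, Barthel Index) are not touched.

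**Working it through.** Neither document states a power, error rate or sample size for fNIRS. The Protocol's sample size calculation concerns PHQ-9 only, so there is no planned figure to reproduce here.

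**Step 1. What is fixed?**

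| Place | Left OFC | Right OFC | Ventrolateral PFC | Dorsolateral PFC | Wording | Metric |
|---|---|---|---|---|---|---|
| Protocol, Neuroimaging Biomarkers | yes | no | yes | no | examples | mean |
| SAP 3 | yes | yes | no | yes | examples, called predefined | mean or peak |
| SAP 4.5 | yes | yes | yes | no | open-ended, *might* average | mean |

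Four regions are named in all, and no single place lists all four. No side is given for ventrolateral or dorsolateral PFC, and the device's 48 channels are not mapped to regions. Left OFC is the only region in all three lists.

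**Step 2. Where could the preliminary results come from?** Both are described by arm: an increase relative to control, and a cutoff for the experimental group. Neither document describes a two-arm pilot. The Protocol places the trial in 2021 to 2022, and SAP 4.8 names a 2023 MATLAB release, so trial data could have existed when the SAP was written. That shows opportunity, not source.

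**Step 3. Chance of a false-positive highlight across regions.** Assume no effect in any region, a two-sided 0.05 test in each, k = 4, and that the best result is highlighted.

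- Independent regions: 1 - (1 - 0.05)^4 = 1 - 0.8145 = 18.5%.
- Equally correlated normal test statistics, by simulation of P(max |Z| > 1.96): 15.6% at correlation 0.5 and 13.0% at 0.7.

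The correlations are assumptions, because the documents give none.

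**Step 4. Leaving mean or peak open as well.** This gives eight statistics, a mean and a peak for each region. Mean and peak of one signal must be strongly related, so I assumed a correlation r of 0.8 to 0.95 between them. The correlation between one region's mean and another's peak was set to the between-region correlation times r.

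| Between-region correlation | r = 0.8 | r = 0.95 |
|---|---|---|
| 0 | 27.9% | 23.4% |
| 0.5 | 23.3% | 19.5% |
| 0.7 | 19.6% | 16.5% |

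The range is therefore roughly 16 to 28%.

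**Step 5. Testing again in overlapping data.** Suppose the preliminary analysis used a share f of this trial's information, and left OFC was singled out because it was significant in the favourable direction. With no true effect, Z_final = √f × Z_prelim + √(1 - f) × Z_rest. By simulation, P(Z_final > 1.96 given Z_prelim > 1.96) is 34% for f = 0.5 and 53% for f = 0.75. It is 100% if the data are the same. Fresh data would give 2.5% in that direction.

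**The case against.** The strongest reply is that the plan already calls this work exploratory. The Protocol says fNIRS will not serve as a primary endpoint, SAP 3 and 4.7 use the same label, and secondary objective 2 is worded as exploration. This stands, and it limits the point: no primary conclusion changes, and requiring a formal multiplicity adjustment would be partly a matter of preference. The label does not, however, tell a reader that the effect may already have been seen in the same data. The Protocol also states a directional fNIRS hypothesis.

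A reader might infer from the differing lists that left OFC was picked from the data. The lists do not support that, because left OFC is in all of them. The possibility of selection rests only on the two preliminary-analysis statements in SAP 4.5.

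A reader might also infer that the trial data were examined before the SAP was final, that SAP 1 is therefore contradicted, and that the statistician's blinding described in the Protocol was broken. The documents do not say which data were used. An undescribed pilot would remove the conflict, and prior evidence in SAP 3 may simply mean published work. The conflict with SAP 1 is conditional, and the blinding inference needs still more that is not in the text.

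Finally, treating all eight region-metric combinations as independent would give 1 - 0.95^8 = 33.7%. That figure should not be used, because mean and peak of one signal are not independent.

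**Conclusion.** The point holds for exploratory outcomes. SAP 3 and SAP 4.5 together present as predefined an effect that the SAP says has already been seen, and they do not identify the data. If the source is this trial, SAP 4.5 conflicts with SAP 1, and neither the left OFC test nor the -0.47 cutoff is independent evidence. If left OFC was fixed beforehand on external data, its error rate is the nominal 5%, and one sentence naming the source settles that half of the concern.

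The open test family is a defect whichever source is disclosed. The false-positive chance is about 19%, 16% and 13% at between-region correlation 0, 0.5 and 0.7, and roughly 16 to 28% with the metric also open. These figures assume the four named regions are the whole family, no effect in any of them, and that the best result is highlighted. They measure the room the wording leaves for selective reporting. They do not show that selection took place.

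**What to change.** In SAP 3 and 4.5:

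- **Source.** State the data and date behind both preliminary results (the group-by-time effect and the cutoff). If they come from this trial, correct SAP 1, label both as data-derived, and do not describe them as predefined or verified.
- **Regions and metric.** Use one closed list made of the regions already named, with side and channels stated. Use one metric, the mean task-minus-rest HbO₂ change. Delete *or peak*, *etc.* and *might*, and make the Protocol's list match.
- **Reporting.** Give the 6-month group-by-time estimate with a 95% CI for every listed region. Either add multiplicity-adjusted p-values (Holm or permutation max-T) or state that the p-values are unadjusted and hypothesis-generating.

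The cost is small. SAP 4.5 already makes the region-level values its analysis variables, so the change is mostly wording and slightly more reporting. The downside for the authors is a less favourable statement about left OFC.

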Hypotheses: We hypothesize that stroke survivors receiving the combined MI and home-based rehabilitation intervention will show significantly greater improvements in mental health outcomes (lower Patient Health Questionnaire-9 depression scores and Fatigue Severity Scale scores, improved Mini-Mental State Examination scores) and physical function (higher Barthel Index scores) over 6 months, compared to those receiving standard care. We also hypothesize that the intervention group will exhibit measurable increases in prefrontal cortical activation (oxyhemoglobin levels) on fNIRS correlating with reduction in depressive symptoms, and that specific fNIRS-derived metrics will predict depression remission status with reasonable accuracy.

Study Design

This study is a single-center, parallel-group randomized controlled trial with a 1:1 allocation ratio to intervention versus control. The trial was conducted at the Vietnam National Geriatric Hospital from 2021 to 2022. A total of 92 stroke survivor participants were enrolled and randomly assigned to either the Intervention group, which received a multi-component program (Motivational Interviewing plus a home-based rehabilitation regimen), or the Control group, which received standard care and general health advice. The study duration for each participant is approximately 6 months, with assessments at baseline and follow-up at 1, 3, and 6 months post-enrollment. Figure 1 presents the planned participant flow per CONSORT guidelines (see Schedule of Events below for timeline of activities). The trial is open-label: due to the nature of the interventions, neither participants nor intervention providers were blinded to group assignment. To reduce potential bias, outcome assessments were standardized, and the data analyst/statistician remained blinded to group labels during analysis.

Eligibility Criteria

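### The planned fNIRS–PHQ-9 change correlation has no arm term, so a treatment effect on both measures can produce a positive result with no association among patients in the same arm

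*SAP*

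**What the plan says.** Under Correlation with Clinical Outcomes, SAP 4.5 plans Pearson or Spearman correlations between changes in fNIRS metrics "and changes in clinical scores (e.g., PHQ-9 drop) across individuals". The paragraph has no arm term, no stratification and no within-arm estimate. The GEE paragraph just above it does include group. Two readings of the result are fixed in advance. On direction: "A positive correlation would indicate that participants with larger brain activation increases tended to have greater depression improvement, supporting fNIRS as a biomarker". On evidence: "A small p-value would suggest significance of this correlation".

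Elsewhere the plan expects treatment to move both variables. For PHQ-9, Protocol, Sample Size and Justification, says: "we assumed a difference in mean PHQ-9 reduction of approximately 3.43 points with a standard deviation of about 5.5". For oxyhaemoglobin, SAP 4.5 anticipates a group-by-time effect in the left orbitofrontal cortex, in which the intervention group's signal "increases over time relative to control (as observed in preliminary analyses".

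The hypothesis behind the correlation is in the Protocol, Trial Objectives and Hypotheses. Its subject is the intervention group, which is expected to "exhibit measurable increases in prefrontal cortical activation (oxyhemoglobin levels) on fNIRS correlating with reduction in depressive symptoms". The SAP does not carry that restriction into the analysis. The Protocol (Outcome Measures) and the SAP (section 3) both label the fNIRS endpoints exploratory.

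**The concern.** A correlation across two arms mixes two sources of covariation. One is whether, among patients treated alike, those whose oxyhaemoglobin rises more also improve more in mood. The other is the distance between the arm means: if the intervention group is higher on both measures, the two clouds of points line up along a rising diagonal and the overall correlation is positive.

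The second source says only that treatment moved both measures. The separate group-by-time models already test that, so the correlation would partly repeat their result in the form of patient-level evidence. The SAP's reading does not separate the two sources. The ambiguity is greatest when the intervention works as hoped, because then both arm differences are present. At stake is the biomarker interpretation, which is part of a stated secondary objective.

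**Working it through.** **Inputs**

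- PHQ-9 effect: 3.43 points, SD 5.5 (Protocol, Sample Size and Justification), so d1 = 3.43/5.5 = 0.624.
- Oxyhaemoglobin effect d2: the documents give direction only. Assumed range 0 to 1.0.
- Allocation 1:1 (Protocol, Study Design), 46 per arm, N = 92.
- Two-sided 5% level (SAP 4.1).
- Within-arm correlation set to zero, to isolate what the arm difference alone produces.

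**The plan's own figure first.** The documents give no figure for the correlation, but the sample size rests on the same PHQ-9 inputs. The Protocol reports that "the estimated minimum sample required was 43 patients per group". The normal formula gives n = 2 × [5.5 × (1.960 + 0.842)/3.43]² = 40.4, so 41 per group. The t-based version gives 41.3, so 42. Both are within two patients of 43, and power is 0.82 at 43 per group and 0.85 at 46. The planned d of 0.624 is therefore a fair input.

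**Induced correlation.** Score PHQ-9 change as a drop, as in the SAP's example, so that both effects are positive. Scale each change by its within-arm SD. With equal arms, the arm difference adds d²/4 to each variance and d1 × d2/4 to the covariance. With within-arm correlation r_w,

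r = (r_w + d1·d2/4) / √[(1 + d1²/4)(1 + d2²/4)].

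With r_w = 0 and d2 = d1 = 0.624, the numerator is 0.0973 and the denominator 1.0973, so r = 0.089. With d2 = 1.0, the numerator is 0.156 and the denominator √(1.0972 × 1.25) = 1.171, so r = 0.133. The added term vanishes only if treatment leaves at least one of the measures unmoved.

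**Rejection rates.** These come from 20,000 simulated normal trials per setting, with d1 = 0.624 and zero within-arm association:

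| Assumed d2 | Induced r | Pearson, 46 per arm | Pearson, 43 per arm | Arm-adjusted, 46 per arm |
|---|---|---|---|---|
| 0 | 0.00 | 5.0% | 5.0% | 4.9% |
| 0.2 | 0.03 | 5.9% | 5.7% | 5.3% |
| 0.5 | 0.07 | 10.5% | 10.2% | 5.1% |
| 0.624 | 0.09 | 13.2% | 12.7% | 5.0% |
| 0.8 | 0.11 | 18.6% | 17.3% | 5.0% |
| 1.0 | 0.13 | 24.4% | 23.3% | 4.9% |

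Spearman rates are within half a percentage point of Pearson, so the choice of coefficient does not help. From d2 = 0.5 upward nearly all rejections are in the positive direction, the one the SAP reads as support. A Fisher z check agrees: at r = 0.089 and N = 92, atanh(r) × √89 = 0.84, which gives a two-sided rejection rate of about 13%. The arm-adjusted correlation averages 0.00 in every row.

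**The case against.** **The SAP never says the arms are pooled.** This is correct. Pooling is the plain reading of a correlation over individuals with no mention of arm, but it remains a reading. Run in the intervention arm alone, as the Protocol hypothesis is worded, the artefact would not arise. The SAP does not impose that restriction, so the gap is real, but it should be described as an omission and not as a stated decision to pool.

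**The SAP's sentence describes a marginal association.** Taken literally, it says that patients with larger activation increases tended to improve more. That is true of the combined sample even when treatment drives it, so rejecting a zero marginal correlation is not a false positive. The Protocol's Background and Rationale also presents fNIRS as a marker of improvement in response to the intervention, and for such a marker covariation caused by treatment is of interest. This stands in part. The rates above are error rates only for the patient-level, arm-conditional question. But a purely marginal result adds little to the group-by-time tests and does not show that oxyhaemoglobin change tracks mood among patients.

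**Larger figures are tempting.** With d = 1.0 on both measures, the induced r is 0.20 and the rejection rate about 48%. A reader might take that as the exposure, but it raises the PHQ-9 effect well above the planned 0.62. At the planned effect the rate for the same d2 is about half that.

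**The consequence is small.** At d = 0.62 on both measures the induced r of 0.09 is under 1% of variance. The analysis is exploratory, and the group-by-time result for oxyhaemoglobin would be visible beside it. All of this stands and limits the weight of the point. It does not correct the reading, because the SAP's significance statement rests on the p-value.

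**Conclusion.** The point holds as a limited one. With no arm term, the planned correlation can be positive and nominally significant because of the treatment difference alone. At the planned PHQ-9 effect, with N = 92 and no within-arm association, the induced r is about 0.03 to 0.13. The rejection rate is about 6% to 24% for an assumed oxyhaemoglobin effect of d = 0.2 to 1.0. Missing 6-month fNIRS recordings would lower these rates slightly, as the 43-per-arm column shows. The figures assume normal changes, equal arms and an effect size that the documents do not give; if treatment does not move oxyhaemoglobin, there is no inflation.

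A reader might infer that the two changes are unrelated within patients, that the biomarker hypothesis is wrong, or that the efficacy results are compromised. The documents support none of these. Each patient contributes one pair of changes, so the relevant condition is no association within arms. Whether that condition is true is unknown before the data are analysed. The primary analyses of the four clinical scales do not use this correlation.

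**What to change.** In SAP 4.5:

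- State which arms enter the correlation.
- Base any patient-level biomarker statement on the correlation adjusted for arm (the partial correlation), reported with its 95% CI.
- Show the two within-arm correlations. The intervention-arm one answers the Protocol hypothesis as worded.
- Report the correlation over both arms descriptively, noting that it includes the treatment difference.

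This needs no new data and costs one degree of freedom (89 in place of 90 with 92 complete pairs). If oxyhaemoglobin change does track mood in individuals, the association also appears within arms, so the adjusted analysis can still detect it. Adding baseline PHQ-9 and baseline oxyhaemoglobin as covariates is optional; arm adjustment alone removes the problem described here.
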